8.7.4 Analysis of exploratory endpoint(s)

Not Applicable.

8.7.5 Subgroup analyses

Subgroup analyses of important factors, including but not limited to factors such as age group, gender, race, and ethnicity are planned for the key outcomes of TEAR rate and immunogenicity variables. Wald confidence limit method for TEAR rate will be used for 90% confidence interval. Other exploratory subgroup analyses may be performed, as deemed appropriate.

The following subgroups will be assessed and described within the subgroup analysis. A minimum of 8 subjects/arm in each subgroup is needed. For subgroup with less than 8 subjects/arm, this subgroup will be pooled with the other ones having less than 8 subjects/arm together and the subgroup will be named “other” if there are other subgroups with less than 8 subjects/arm exist.

- Gender:
 - o Female
 - o Male
- Age (years):
 - o ≤ 21
 - o > 21 to <65
 - o ≥ 65
- Race:

- o American Indian or Alaska Native
- o Asian
- o Black or African American
- o Native Hawaiian or Other Pacific Islander
- o White
- Ethnicity:
 - o Hispanic or Latino
 - o Not Hispanic or Latino
 - o Not reported or Unknown

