5 SAMPLE SIZE AND POWER

Approximately 500 subjects with type 1 diabetes will participate in this trial. The sample size estimation is based on primary objective - to demonstrate that immunogenicity as assessed by TEAR rate with MYL-1601D is equivalent to that of NovoLog® during 24-week treatment. The 80% power will be achieved with 250 subjects per treatment arm to demonstrate that 90% confidence interval of treatment difference (MYL-1601D minus NovoLog®) is within prespecified \pm margin (Table 2 of the SAP) (Chow SC et al, 2002; Chow S-C et al 2003). The pre-specified equivalent margin is dependent on the final rate of NovoLog® TEAR rate. No replacement of subject will be performed if subject discontinued prematurely from the study.

Table 2: Margins and 95% CIs with different reference TEAR event rates in 500 subjects

Event Rate for Reference Product	Estimated 95% CI for the Event Rate (n=250)	Margin	Type I error 2 one-sided alpha	Power	Total N
5%	(2%,8%)	5.7%	0.05	80%	500
10%	(6%,14%)	7.9%	0.05	80%	500
15%	(11%,19%)	9.3%	0.05	80%	500
20%	(15%,25%)	10.5%	0.05	80%	500
25%	(20%,30%)	11.3%	0.05	80%	500
30%	(24%,36%)	12.0%	0.05	80%	500
35%	(29%,41%)	12.5%	0.05	80%	500
40%	(34%,46%)	12.8%	0.05	80%	500
45%	(39%,51%)	13.0%	0.05	80%	500
50%	(44%,56%)	13.1%	0.05	80%	500
55%	(49%,61%)	13.0%	0.05	80%	500
60%	(54%,66%)	12.8%	0.05	80%	500

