If the subject was ADA positive at baseline, then the imputed titer values will be used. The subject will be considered TEAR positive if the ADA titer at any post-baseline visit was $\geq 4\times$ the baseline titer. If none of the post-baseline titer values reached 4 times the baseline titer, then the subject will be classified as TEAR negative.

For each imputation, the proportion of responders, along with standard errors, will be estimated for each treatment group, and the estimate and standard error of the risk difference will be computed. These values will be combined across imputations using PROC MIANALYZE. Subsequently, the 90% confidence interval for the risk difference will be computed using the Wald confidence limit method.

An equivalence margin will be established as a function of the TEAR rate among the Novolog subjects. Under the null hypothesis of equivalence (i.e., $H_0: p_M = p_N$), the margin can be obtained as a function of the TEAR rate in the Novolog group using the following expression (Chow S-C et al., 2003, p. 91).

$$\delta = (z_\alpha + z_\beta) \sqrt{\frac{2p_N(1 - p_N)}{n_N}}$$

Selected values for δ are provided in Table 2 of Section 5 above. If the margin falls within the 90% confidence interval for the risk difference, then equivalence of MYL1601-D and Novolog will be declared.

These steps can be executed using code similar to the following:

```
proc freq data=simdata ;
title "90% Wald confidence interval";
by _imputation_;
ods output riskdiffcol2=rdiff1;
table group*resp / riskdiff (CL=WALD column=2) alpha=0.1;
weight count;
run;

data rdiff1; set rdiff1;
keep _imputation_ row risk ase lowercl uppercl;
if row='Difference';
run;

proc mianalyze data=rdiff1;
modeleffects risk;
stderr ase;
ods output ParameterEstimates=mirisk1;
run;

ods listing;
data parms1;
set mirisk1;
lowercl = estimate - (1.645*stderr);
uppercl = estimate + (1.645*stderr) ;
run;
proc print data=parms1;
var estimate stderr lowercl uppercl;
run;
```

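### Subgroup TEAR differences get Wald 90% intervals in groups as small as 8 per arm, where the interval shrinks to zero width if both arms are at 0% or both at 100%; a reporting problem only, and rare unless TEAR rates are low

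*SAP*

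**What the plan says.** SAP 8.7.5 plans subgroup analyses of TEAR by gender, age, race and ethnicity, and allows further exploratory ones. On method: "Wald confidence limit method for TEAR rate will be used for 90% confidence interval". Protocol 7.2.6 gives the same rule.

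On size: "A minimum of 8 subjects/arm in each subgroup is needed". A subgroup below the floor is merged with others below it, and the result "will be named “other” if there are other subgroups with less than 8 subjects/arm exist". No rule is given for a single small subgroup with nothing to merge with.

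The Wald code appears in SAP 8.7.2.1, for the primary analysis. Within each imputation it runs "table group*resp / riskdiff (CL=WALD column=2) alpha=0.1", passes the risk difference and its standard error to PROC MIANALYZE, and forms limits of the type "lowercl = estimate - (1.645*stderr" with the matching upper limit. SAP 8.7.5 does not say whether subgroups use the imputed or the observed data.

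Neither document offers a small-sample interval, or a rule for arms with no events or all events. Neither sets a margin or an equivalence decision for subgroups.

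**The concern.** The Wald standard error is built from the observed proportions, so an arm at 0% or 100% contributes no variance. If both arms sit at the same boundary, the interval is a single point at zero. This hardly matters at 250 per arm, but it can matter at 8.

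Small cells are plausible. The SAP lists five race and three ethnicity categories. It also lists an age group of 65 and over, although Protocol 4.2.1 limits entry to ages 18 to 65, so only 65-year-olds can fall in it.

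At stake is the precision shown in the subgroup table. A group with no TEAR in 16 subjects could print a difference of 0.0% (0.0%, 0.0%), the narrowest interval on the page, where the information is weakest.

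**Working it through.** **Inputs.** Two-sided 90% Wald interval and a floor of 8 per arm (SAP 8.7.5); critical value 1.645 (SAP 8.7.2.1); 250 per arm for the whole trial and reference TEAR rates from 5% to 60% (SAP Section 5, Table 2). No expected TEAR rate is stated, so rates from the Table 2 range are taken as assumptions. Both arms are set to n = 8.

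**The plan's own figures.** The margin formula in SAP 8.7.2.1, with the quantiles in the SAP 10.2 code, is δ = (z0.95 + z0.90)·√(2p(1−p)/250). At p = 5%: 2.926 × √0.00038 = 5.70%; Table 2 shows 5.7%. At p = 50%: 2.926 × √0.002 = 13.1%; Table 2 shows 13.1%. All 12 rows agree to within 0.05 points. The full-sample design is not in question.

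**Single tables at 8 per arm.** Wald: d ± 1.645·√(p1(1−p1)/8 + p2(1−p2)/8).

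- 0/8 vs 0/8 (and 8/8 vs 8/8): the standard error is 0, so the interval is [0, 0].
- Newcombe for 0/8 vs 0/8: the Wilson upper limit for 0/8 is 1.645²/(8 + 1.645²) = 2.706/10.706 = 25.3%, so the interval is ±25.3 points. Miettinen-Nurminen gives ±26.5 points.
- 1/8 vs 1/8: Wald ±27 points. 2/8 vs 2/8: ±36. 4/8 vs 4/8: ±41.

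**Chance of [0, 0] with equal true rate p.** (1−p)^16 + p^16, where the second term is negligible at low rates: 0.95^16 = 0.440; 0.90^16 = 0.185; 0.80^16 = 0.028; 0.70^16 = 0.0033. At 40–50% it is 0.03% or less.

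**Coverage.** Sum Bin(a; 8, p1)·Bin(b; 8, p2) over all 81 tables (a, b) whose interval contains p1 − p2.

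| True rates | Wald | Newcombe |
|---|---|---|
| 5% vs 5% | 99.2% | 99.2% |
| 10% vs 10% | 96.3% | 96.7% |
| 20% vs 20% | 89.3% | 92.4% |
| 30% vs 30% | 86.4% | 91.8% |
| 5% vs 20% | 79.0% | 93.4% |
| 10% vs 30% | 81.6% | 92.9% |
| 30% vs 50% | 85.8% | 88.4% |

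With equal low rates Wald coverage is high because [0, 0] contains the true difference of zero. With unequal rates the same table is a miss: at 5% vs 20% it occurs with probability (0.95 × 0.80)^8 = 0.76^8 = 0.111, about half of the 21% total non-coverage.

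**Larger groups.** At 5% in both arms the chance of [0, 0] is 0.95^24 = 29% at 12 per arm, 0.95^40 = 13% at 20 and 0.95^100 = 0.6% at 50. Wald coverage is 88–91% at 50 per arm and about 90% at 250.

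**The case against.** The strongest reply is that this needs two conditions the documents do not establish: a subgroup near 8 per arm and a TEAR rate around 5–10%. TEAR is cumulative over seven post-baseline samples, so the rate may be well above that, and over most of the Table 2 range zero width is rare. This stands, and is why the full range of rates is shown.

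Three stronger readings are tempting, and the documents do not support them.

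- A reader might infer that Wald under-covers wherever it collapses. It does not: with equal rates of 5–10% its coverage is above nominal. The fault there is false precision in particular tables; low coverage comes mainly with unequal rates.
- A reader might infer that the smallest subgroups will always show the tightest intervals. Only boundary tables do; one event per arm already gives ±27 points. SAP 8.1 also calls for counts and percentages, so 0/8 and 0/8 should be visible beside the interval.
- A reader might lay a subgroup interval against the Table 2 margin and see equivalence shown or lost. The plan provides no such test. Its margin is for the overall comparison ("The pre-specified equivalent margin is dependent on the final rate of NovoLog® TEAR rate"), and SAP 8.7.1 declares equivalence from the ITT population as a whole.

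If imputed data are used and a subgroup has missing TEAR status, between-imputation variance could also keep the interval from being exactly zero. That is fair, but it depends on missing data falling in that subgroup and would not make the width right.

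**Conclusion.** The point holds as a reporting-precision problem in small subgroups, of low to moderate weight. Applied as written, the rule can print a zero-width interval where a score-type method gives about ±25 points. At 8 per arm with equal true rates, the chance runs from 44% at a TEAR rate of 5% to 0.3% at 30%. Where the true rates differ, coverage falls short of 90% by about 11 points (5% vs 20%), 8 points (10% vs 30%) and 4 points (30% vs 50%).

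These figures assume exactly 8 per arm, independent binomial outcomes, observed data and plain Wald without a continuity correction. The documents forecast neither the TEAR rate nor the subgroup sizes. The primary analysis, its margin and its conclusion are unaffected.

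**What to change.** In SAP 8.7.5, replace Wald with a Newcombe or Miettinen-Nurminen 90% interval for subgroup risk differences, and state whether subgroups use observed or imputed data.

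- **Observed data:** a change of option, for example `riskdiff(cl=newcombe)` in PROC FREQ, and one sentence of text.
- **Imputed data:** name a score or Wilson-type interval compatible with multiple imputation. Changing the PROC FREQ option alone would do nothing, because the reported limits are rebuilt after PROC MIANALYZE as the pooled estimate ± 1.645 standard errors.

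Keep Wald for the full-sample primary analysis.

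The cost is wider intervals in small subgroups and slightly more programming if imputation is used. Newcombe is not exactly 90% everywhere either (lowest value on the grid tried at 8 per arm: 84%), but it does not collapse to zero width. Protocol Section 7 lets the SAP modify the planned analyses and reserves amendments for major changes to the primary endpoint or its analysis, so a SAP revision should be enough.

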4.2 Inclusion and Exclusion Criteria

4.2.1 Inclusion Criteria

Subject eligibility should be reviewed and documented by an appropriately qualified member of the Investigator's study team before subjects are included in the study.

Subjects must meet all of the following inclusion criteria to be eligible for enrolment into the study:

1. Written and signed informed consent needs to be provided by subjects before starting any protocol-specific procedures.
2. Male and female subjects between the ages of 18 to 65 years, both ages inclusive.
3. Clinical diagnosis of type 1 diabetes mellitus for at least 6 months or more prior to screening.
4. Stable dose of once daily basal Lantus® or Toujeo® injection and multiple daily bolus NovoLog® or Humalog® injections for at least 3 months at screening.
5. Body mass index (BMI) of 18.5 to 35.0 kg/m² at screening (both values inclusive).
6. Stable weight, with no more than 5 kg gain or loss in the 3 months prior to screening (collected by subject interview during medical history).
7. Glycosylated hemoglobin (HbA1c) 6.5-10.0 % at screening.
8. Hemoglobin \geq 10.0 g/dL at screening.
9. Subject has the capability of communicating appropriately with the Investigator.
10. Subject is able and willing to comply with the requirements of the study protocol including the 7-point self-monitored blood glucose (SMBG), completion of subject diary records and following a recommended diet and exercise plan for the entire duration of the study.
11. Female subjects of childbearing potential who are willing to use oral contraception or acceptable methods of contraception, (e.g., intra-uterine device, spermicidal gel plus condom, diaphragm plus condom, etc.), from the time of screening and for the duration of the study, through study completion.
 - a. Periodic abstinence (e.g., calendar, ovulation, symptothermal, post-ovulation

methods) and withdrawal are not acceptable methods of contraception.

- b. Postmenopausal females must have had no regular menstrual bleeding for at least 1 year prior to screening.
- c. Female subjects who report surgical sterilization must have had the procedure at least 6 months prior to screening.
- d. All female subjects of childbearing potential must have negative pregnancy test results at screening and at clinic visits, as per the SCHEDULE OF ACTIVITIES (SOA).
- e. If female subjects have male partners who have undergone vasectomy, the vasectomy must have occurred more than 6 months prior to screening

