6.1.1 Screening (Visit 1 [Week -7 to Week -4])

Subjects will commence screening procedures within up to 7 weeks prior to randomization, to confirm that they meet the selection criteria for the study. If the time between screening procedures and the run-in period exceeds 3 weeks, due to unexpected delays, drop out, or any other reason, the subject can be rescreened one time based on discussion between the site or designee and with Mylan personnel. In case re-screening is agreed, the subject will need to be re-consented and assigned a new SID via IWRS. If re-screening occurs, the reason and approval needs to be clearly documented within the site file.

The following will be completed during the visit:

- Obtain written informed consent before any study-related procedure is initiated, including the cessation of prohibited concomitant therapy. A copy of the signed ICF (including subject information sheet) will be given to the subject.
- Check eligibility criteria.
- Record detailed history of all previous insulin use (as far as the patient can remember).
- Perform dilated ophthalmoscopy / retinal photography (if it was not done in the last 6 months) to exclude active proliferative retinopathy.
- Discuss and check compliance to standard of care specifics as per American Diabetes Association 2019 guidelines, self-management of diabetes and life-style modifications with the subject.
- Record demographic details (age, gender, height, and race).
- Record body weight and calculate BMI.
- Record medical history, concomitant illnesses and concomitant medications.
- Record vital signs (sitting after 5 minutes rest; pulse, blood pressure, temperature and respiratory rate).
- Perform and document physical examination.
- Perform 12-lead ECG (supine, after 5 minutes rest) and document results.
- Collect blood and urine samples for the following laboratory assessments:
 - Fasting C-peptide
 - Serum pregnancy test for women of childbearing potential
 - HIV, HBsAg, and HCVAb
 - Hematology
 - Blood chemistry
 - Urine analysis
 - HbA1c
 - Fasting plasma glucose
 - Immunogenicity analysis
- Record AEs, SAEs, local and systemic allergic reactions and hypoglycemic events which occur after time of informed consent signature.

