7.2.6 Sub-Group Analyses

Subgroup analyses of important factors, including but not limited to factors such as age group, gender, race, and ethnicity are planned for the key outcomes of TEAR rate. Wald confidence limit method for TEAR rate will be used for 90% confidence interval. Other exploratory subgroup analyses may be performed, as deemed appropriate.

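### The oldest age subgroup (65 and over) can hold only subjects aged exactly 65, and the SAP's pooling rule handles so small an age level poorly or not at all

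*SAP*

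**What the plan says.** Protocol 4.2.1, criterion 2, admits "Male and female subjects between the ages of 18 to 65 years, both ages inclusive". Age is taken at the screening visit (Protocol 6.1.1: "Record demographic details (age, gender, height, and race").

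Protocol 7.2.6 states that "Subgroup analyses of important factors, including but not limited to factors such as age group, gender, race, and ethnicity are planned" for the TEAR rate, with 90% Wald intervals. SAP 8.7.5 repeats this and lists the levels. For age they are ≤21, >21 to <65, and ≥65.

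SAP 8.7.5 also sets a size rule for all factors: "A minimum of 8 subjects/arm in each subgroup is needed". A level that falls short is dealt with as follows: "For subgroup with less than 8 subjects/arm, this subgroup will be pooled with the other ones having less than 8 subjects/arm together". The new group depends on a condition: "the subgroup will be named “other” if there are other subgroups with less than 8 subjects/arm exist".

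Randomization is stratified by investigator and basal dose time (SAP 3.2.1), not by age. Neither document gives an expected age distribution.

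**The concern.** Set side by side, the entry cap and the age levels do not fit. Among eligible subjects ≥65 is one year of age, ≤21 is four years (18 to 21), and the middle level is the other 43.

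The size rule does not repair this. It joins small levels whether or not they are adjacent, which is reasonable for an unordered factor such as race but not for age. It also acts only when at least two levels are small, so a single small level has no stated treatment.

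Age is one of four factors named for the TEAR subgroup analyses. At stake is whether the prespecified output can show anything about how the treatment difference in TEAR varies with age. If the gap is left until treatment codes are known, any repair becomes a post hoc choice of age groups.

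**Working it through.** **Inputs.** 250 subjects per arm (SAP 5: "The 80% power will be achieved with 250 subjects per treatment arm"); entry ages 18 to 65, which is 48 whole years; minimum of 8 per arm (SAP 8.7.5); 90% intervals. Age shares and the TEAR rate used for precision are assumptions.

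**1. The plan's own margin as a yardstick.** SAP 10.2 codes δ = (z₀.₉₅ + z₀.₉₀)·√(2p(1−p)/n). At p = 20% and n = 250 this is (1.645 + 1.282) × √(0.32/250) = 10.5 points, as in SAP Table 2. The sample size is not in question.

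**2. Expected numbers per arm if ages are flat.**
- Age 65: 250 × 1/48 = 5.2
- Ages 18 to 21: 250 × 4/48 = 20.8
- Ages 22 to 64: 250 × 43/48 = 224, or 89.6%

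**3. Chance that a level has fewer than 8.** The count in one arm is Binomial(250, share). With P = Pr(count ≤ 7), the chance for at least one arm is 1 − (1 − P)².

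| Level | Assumed share | Expected per arm | <8 in a given arm | <8 in at least one arm |
|---|---|---|---|---|
| Age 65 | 1% | 2.5 | 0.996 | >0.99 |
| Age 65 | 2.1% (flat) | 5.2 | 0.85 | 0.98 |
| Age 65 | 3.2% | 8.0 | 0.45 | 0.70 |
| Ages 18–21 | 2% | 5.0 | 0.87 | 0.98 |
| Ages 18–21 | 3.2% | 8.0 | 0.45 | 0.70 |
| Ages 18–21 | 4% | 10.0 | 0.21 | 0.38 |
| Ages 18–21 | 5% | 12.5 | 0.065 | 0.13 |
| Ages 18–21 | 8.3% (flat) | 20.8 | 0.0003 | 0.0006 |

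To expect 8 per arm, 65-year-olds would have to be 8/250 = 3.2% of subjects, about 1.5 times the flat share.

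**4. Which branch of the rule applies.**
- *Both end levels small.* They are joined, so 18-to-21-year-olds and 65-year-olds form one group. This becomes likely only when ages 18 to 21 are roughly 3 to 4% of subjects or less.
- *Only the 65 level small.* This is the likely case under flat ages. The condition for forming a pooled group is not met, and no other instruction is given.

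**5. Precision of what would be reported.** The 90% Wald half-width is 1.645 × √(2p(1−p)/n), here with the same rate in both arms.

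| n per arm | p = 20% | p = 5% to 50% |
|---|---|---|
| 8 (SAP minimum) | 32.9 points | 17.9 to 41.1 |
| 21 (ages 18–21, flat) | 20.3 | 11.1 to 25.4 |
| 224 (ages 22–64, flat) | 6.2 | 3.4 to 7.8 |

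For the whole trial at 20% the half-width is 1.645 × √(0.32/250) = 5.9 points. The middle level is close to a copy of the overall analysis.

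**The case against.** The strongest reply is that this is a descriptive analysis with low stakes, and that the damage is easily overstated. Three stronger readings are tempting, and the documents do not support them.

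- *No usable age comparison is left.* A reader might infer this, but it does not follow. With flat ages, 18 to 21 has about 21 per arm, clears the minimum and stays separate. The comparison of ≤21 with >21 to <65 then remains, at about ±20 points within the younger level if the TEAR rate is 20%. Even if the end levels merge, the treatment comparison within the middle level survives.
- *The youngest and oldest will be merged.* The rule permits this but does not make it certain. It depends on an age distribution that the documents do not give.
- *The SAP prescribes a Wald interval on a handful of 65-year-olds.* It does not. The stated minimum could equally mean that a lone small level is not analysed. The defect is silence.

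It is also true that both documents allow further exploratory subgroups, so other age cuts are open, though not prespecified. No subgroup equivalence decision or interaction test is planned. The pooling rule is sensible for race; what is missing is an exception for an ordered factor.

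All of this limits the size of the point. None of it removes the mismatch between the entry cap and the top level, the lack of an adjacency requirement, or the missing instruction for a single small level.

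**Conclusion.** The point holds as a minor design flaw in a descriptive analysis. That ≥65 means exactly 65 follows from the text alone, apart from enrolment deviations or a 66th birthday if age were derived after screening. That the level falls below 8 per arm is very likely if 65-year-olds are no more common than under flat ages. Merging with 18-to-21-year-olds is conditional on that level being scarce as well.

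In either case, nearly all subjects sit in one level, so the listed categories say little about whether the TEAR difference varies with age. The primary equivalence test, its margin and the sample size are untouched.

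**What to change.** Before unblinding, amend SAP 8.7.5 in two places.

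1. Replace the age levels with cut points inside the eligible range, for example 18 to <35, 35 to <50 and 50 to 65 years, or a split at the blinded pooled median. These cuts are illustrative. With flat ages the three bands cover 17, 15 and 16 years, giving 250 × 17/48 = 89, 250 × 15/48 = 78 and 250 × 16/48 = 83 per arm. The 90% half-widths at a 20% TEAR rate are then 9.9, 10.5 and 10.2 points.
2. For age, pool any level below 8 per arm only with an adjacent level, including when it is the only small one, and say which neighbour is used if there are two. Keep the existing *other* rule for unordered factors such as race.

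The cost is SAP wording; age is already collected. The downside is that the groups would no longer match a 65-and-over reporting category, which this population cannot fill.
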